5.4 Treatments Administered

Once eligibility is confirmed, patients will be randomized in a 1:1 ratio to one of two treatment arms listed in Table 1. Dosing will be performed twice daily approximately 12 hours apart in the morning and evening at approximately the same time each day.

Table 1. COSTA treatment arms.

Treatment Arm	n	Treatment
Treatment Arm 1	7-8	Blinded alvelestat (240 mg) tablets BID + SoC*
Treatment Arm 2	7-8	Blinded placebo tablets BID + SoC*

Abbreviations: SoC= standard of care, BID= twice daily, *SoC treatment for COVID-19 infection based on established practices within UAB

5.5 Method of Assigning Patients to Treatment Groups (Randomization)

Randomization will take place prior to the first study medication administration in the order patients are enrolled and in accordance with a computer-generated randomization list supplied by the an independent statistician through the UAB Research Pharmacy. Available randomization numbers must be used sequentially for the next enrolled patient. Patients will be dosed with either blinded alvelestat or placebo according to the randomization scheme.

5.5.1 Selection and Timing of Dose for Each Patient

Each patient is randomly assigned 1:1 to a treatment group. Study medication dosing starts on Day 1 after randomization and continues twice daily, approximately every 12 hours, until discharge or Day 10, whichever is first.

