5.0 STUDY DESIGN

5.1 Overall Design and Purpose

This is a Phase Ib/II single-center, 2:1 randomized, blinded, placebo-controlled, parallel group, first in disease study. The purpose is to determine the safety, tolerability and PK and explore the mechanistic and clinical effect of alvelestat 240mg orally twice per day for 5 or 10 days added to standard of care in adult patients (≥ 18 years) with COVID-19 respiratory disease.

The study is divided into 3 periods: a screening period, treatment period, and follow up period ([Figure 1](#))

Figure 1: Study Schematic

- **A screening period** from Day -2 to randomization. Eligibility assessments and written informed consent will occur prior to randomization and treatment arm allocation. Serious Adverse Events will be collected during screening.
- **A treatment period** consisting of alvelestat/matched placebo 240 mg/matched placebo bid Days 1 to 5 given on top of standard of care (SoC – per local clinical guidelines). Safety assessments including vital signs, liver and renal function, EKG, and hematology will be assessed at baseline, then as per the Schedule of Assessments (SoA) for the remainder of the 5-day treatment period. Adverse events, vital signs, respiratory support and concomitant medications that may be part of routine clinical care will be collected daily during hospitalization. Blood will be collected at baseline and during study drug treatment to Day 5 for secondary efficacy biomarkers, along with assessment of oxygen deficit assessments (SaO₂/FiO₂). PK sampling will be collected on 2 occasions, at initiation of dosing and at end of treatment (EoT) for steady state analysis. For patients that remain hospitalized at Day 5 due to COVID-19, an optional extension period of treatment to Day 10 may be given and can be referred to on the separate SOA covering this extension. Clinical outcomes of disease progression (respiratory support requirements), disease severity (WHO ordinal scale), will be completed at Baseline (Day 1), during the treatment period to (Day 5 or 10), or EoT and to Day 60 (Clinical Outcome Assessments). Those subjects who are unable to complete the treatment period for any reason, including those discharged from hospital prior to completion of Day 5 or 10, will discontinue study drug and undergo an EoT assessment. Wherever possible they will continue to be followed up in the study.

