5.4 Scientific Rationale for Study Design

As the first study of alvelestat in the COVID-19 patient population, investigation of safety and tolerability are the primary objectives, and are appropriately investigated in a small 15 subject study. Given the severe nature of COVID-19, alvelestat or identical placebo will be dosed on top of full standard of care. A blinded, placebo-controlled design will support interpretation of safety, tolerability and efficacy biomarkers. Historic comparators were not considered as the evolution of the pandemic and changing management of COVID-19 means that a placebo arm recruited in parallel is a more robust approach.

Neutrophils and NETosis play a critical role in the acute inflammatory response and the most appropriate time to intervene is early in its initiation, to reduce the risks of further progression. Therefore, the target population is those with proven SARS-CoV-2, requiring hospitalization, with evidence of pulmonary disease on chest radiograph or Computerised Tomography (CT) or other relevant imaging, but not progressed to severe disease (i.e. not requiring mechanical ventilation or with multi-organ failure) at the point of recruitment. This population is known to have an acute phase response and evidence for neutrophil activation (raised CRP and absolute neutrophilia, with activation of the NETosis pathway ([Zuo et al 2020](#)), therefore giving potential to detect a mechanistic signal in the study. At this stage neutrophil elastase may be a key pathogenic driver and its inhibition stand the greatest chance of success.

The duration of dosing will be for 5 days with optional extension to 10 days for subjects who remain hospitalized with SARS-CoV2 related disease per investigator decision. Deterioration in COVID-lung disease in hospitalized patients to intubation is rapid and bimodal with modes as 3-4 days and 9 days from the date first symptoms recorded ([Argenziano et al 2020](#)) and even shorter period from date of hospital admission with the most patients worsening within the first 3 days ([Vultaggio et al 2020](#)). With improvements in management of COVID-19 hospital stays have decreased to a mean of 5 days. Therefore, 5 days treatment will provide NE inhibition to cover the critical risk period during hospitalization, with the option to continue to 10 days for those who disease remains active requiring ongoing hospitalization by Day 5.

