7.1 Treatments Administered

There are no bioavailability data to support administration of alvelestat given dissolved in fluid or as broken/crushed tablets for administration via nasogastric or other enteric feeding tube. If participants are unable to swallow tablets orally, study drug treatment needs to be discontinued (Section 8.1).

Study Treatment Name:	30mg alvelestat tablets	Placebo
Dosage Formulation:	Tablet	Tablet (identical in appearance to active)
Unit Dose Strength(s) / Dosage Level(s):	Days 1-5 (or 10): 240mg bid (8 x 30mg tablets bid)	Days 1-5 (or 10): 8 x tablets bid
Route of Administration	Oral	Oral
Dosing Instructions:	To be taken bid, 12 hours apart	
Packaging and Labeling:	Study treatment will be provided in wallets and will be labeled as required per U.S. regulations.	
Manufacturer:	Mereo BioPharma 4 Ltd., [name]	

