5 INVESTIGATIONAL PLAN

5.1 Overall Study Design and Plan

This is a Phase Ib/II single-center, 1:1 randomized, blinded, placebo-controlled, parallel group, first in disease study. The purpose is to determine the safety, tolerability and PK and explore the mechanistic and clinical effect of alvelestat up to 240mg orally twice per day for 10 days added to standard of care in adult patients (≥ 18 years) with COVID-19 respiratory disease.

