7.6 Safety Analysis

Time to first combined event.

Any patients that are lost to follow-up or terminated early prior to experiencing any of the events will be censored at the day of their last observed assessment.

Patients who complete follow-up but do not experience any of the events will be censored at the day of their Day 29 visit.

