8.3 Primary Endpoint Analysis

The primary endpoint is safety and tolerability of alvelestat. Safety endpoints include SAEs and AEs. Adverse events will be analyzed using quantitative and qualitative measures.

Treatment-emergent adverse events will be summarized by treatment group for all AEs, related AEs, serious adverse events, deaths, adverse events leading to discontinuation of study medication or to withdrawal from study, adverse events of different severity and adverse events of different chronicity.

Treatment-emergent adverse events will be coded using MedDRA and summarized by system organ class and preferred term for each treatment group.

The time to the composite AE endpoint (death, SAE, severe AE or ET/W of treatment during first 10 days) will be compared between treatment groups using the log-rank test and difference between treatment arms will be expressed as a difference in proportions as measured by the Cochran Mantel-Haenzel (stratum)-weighted estimator based on the fitted logistic regression model

- If '0' events, proportions will be presented.

Summaries of the results of the safety analysis are displayed in **Table 8**.

Table 8. COSTA analysis tables - Safety Analyses.

Table #	Table Name
	Time to first composite AE (Safety Analysis Set)
	Number/Proportion Treatment emergent adverse events summary (Safety Analysis Set)
	Number/Proportion TEAEs leading to discontinuation of study treatment by system organ class and preferred term (Safety Analysis Set)
	Number/Proportion TEAEs with an outcome of death by system organ class and preferred term (Safety Analysis Set)

Deaths, Serious Adverse Events and other Significant Adverse Events

Narratives will be provided for deaths and serious adverse events.

Pregnancies.

For any patients in the Safety population who become pregnant during the study, every attempt will be made to follow these patients to completion of pregnancy to document the outcome, including information regarding any complications with pregnancy and/or delivery.

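### SAP 5.1, 5.2 and 5.5.1 still state the superseded 10-day course, and the SAP 8.3 safety composite counts an unexpanded ET/W of treatment that is not tied to each patient's planned course

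*SAP*

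**What the plan says.** **Protocol.** The treatment table in section 7.1 gives "Days 1-5 (or 10): 240mg bid (8 x 30mg tablets bid"), and the schedule of assessments puts End of Treatment at Day 5. Section 5.4 allows "optional extension to 10 days for subjects who remain hospitalized with SARS-CoV2 related disease per investigator decision". On discharge, section 5.1 says that patients who cannot complete treatment, "including those discharged from hospital prior to completion of Day 5 or 10, will discontinue study drug".

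**SAP, regimen.** Section 5.1 describes dosing "orally twice per day for 10 days added to standard of care", and section 5.2 repeats 10 days in the primary objective. Section 5.5.1 says dosing "continues twice daily, approximately every 12 hours, until discharge or Day 10, whichever is first". Elsewhere the SAP is up to date: Table 3 (endpoints), Table 4 (disposition) and Table 9 (biomarkers) all work with 5 or 10 days.

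**SAP, analysis.** Section 8.3 compares the arms by log-rank test, and as a difference in proportions, on time to a "composite AE endpoint (death, SAE, severe AE or ET/W of treatment during first 10 days"). ET/W is not in the abbreviation list and is not explained anywhere. It is read here as early termination or withdrawal. Section 7.6 adds: "Patients who complete follow-up but do not experience any of the events will be censored at the day of their Day 29 visit". Table 7 in section 8.2 leaves out doses stopped or missed because of discharge. Section 8.3 has no such clause.

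**The concern.** Finishing a planned 5-day course and going home are not signs of intolerance. The ET/W component has a 10-day window but no statement of what the patient was meant to receive, while the SAP's own dosing section describes a course that most readers of the current protocol would call extended. A programmer has to decide which text governs, and the two texts give different answers for identifiable groups of patients.

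Two things are at stake. A planned or benign stop could enter the composite as a safety event. And because the analysis is time to first event, a false event around Day 5 would take the place of a true serious or severe event, or a death, occurring later in the same patient before Day 29.

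**Working it through.** The documents give no event rate, effect or power for this composite, so there is no planned figure to reproduce. The check is a comparison of texts, followed by simple arithmetic on size.

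**Step 1: which patients are exposed, and under which text**

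| Patient | If SAP 5.5.1 governs | If protocol 5.1 and 7.1 govern |
|---|---|---|
| Completes Day 5, not extended, still in hospital | Stopped before discharge and before Day 10: could be scored ET/W | Planned completion: not an event |
| Completes Day 5, discharged that day | Planned end of dosing: not an event | Planned completion: not an event |
| Discharged before Day 5 | Planned end of dosing: not an event | Called discontinuation: could be scored ET/W |
| Extended, discharged before Day 10 | Planned end of dosing: not an event | Called discontinuation: could be scored ET/W |

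Each governing text exposes a different group, and no row is exposed under both. The first row is foreseeable, because extension is optional and left to the investigator.

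**Step 2: what one misclassified patient does**

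- Protocol 5.2, 10 alvelestat and 5 control: 1/10 = 10.0 points; 1/5 = 20.0 points.
- SAP Table 1, 7-8 per arm: 1/8 = 12.5 points; 1/7 = 14.3 points.

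**Step 3: how many patients**

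Not stated. Protocol 5.4 says "hospital stays have decreased to a mean of 5 days", which suggests that discharge around Day 5 is not rare. But a mean gives no proportion, and stay is counted from admission, not from the first dose.

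**Step 4: direction, on assumed values only**

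Let p be the true risk of a composite event and q the share of event-free patients whose planned or benign stop is scored. The scored risk is p + (1 - p)q.

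- Same q in both arms, assumed p of 0.20 (placebo) and 0.40 (alvelestat), q = 0.50: placebo 0.20 + 0.80 × 0.50 = 0.60; alvelestat 0.40 + 0.60 × 0.50 = 0.70. The difference shrinks from 0.20 to 0.10.
- Different q, same assumed p of 0.20 in both arms, q = 0.25 in one and 0.50 in the other: 0.20 + 0.80 × 0.25 = 0.40 against 0.20 + 0.80 × 0.50 = 0.60. A difference of 0.20 appears where there is none.

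So the error could hide a difference or create one. The documents fix neither p nor q.

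**The case against.** The best case against the point is that the SAP, read as a whole, leads to the sensible answer. Section 5.5.1 itself makes discharge an end of dosing, and Table 7 shows the same intent. Table 4 lists completion of 5 days as a milestone and withdrawn patients as a separate item, so scoring a Day 5 completer as withdrawn would contradict it. Section 7.2 speaks of a maximum of 10 days, which fits the amended course, and section 3 sends the reader to the protocol for study conduct. Early termination is not a natural name for finishing a planned course.

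Most of this stands, and it rules out a stronger reading that a reader might infer: that the SAP has no rule on discharge at all, so that Day 5 completers and patients sent home would both be counted. The documents do not support that. The two misclassifications need different governing texts, and either text applied consistently exposes only one group.

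It is also fair that the composite is not among the protocol's endpoints or its section 10.3.1 methods, that SAP 7.2 calls all analyses exploratory, and that the pilot is unpowered. Table 8's counts of adverse events leading to discontinuation are untouched because they require an adverse event, and the subject listings would help to trace individual cases.

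What the objection does not remove is that sections 5.1, 5.2 and 5.5.1 are out of date, and that section 8.3 does not say which text governs in the only between-arm test it names.

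**Conclusion.** The point holds as a minor inconsistency with a specific route into an analysis. Three SAP sections contradict the current protocol and the SAP's own tables. The ET/W component is undefined and its outcome depends on which text is followed: non-extended Day 5 completers still in hospital under SAP 5.5.1, or patients discharged before Day 5 or during the extension under protocol 5.1.

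The size is 10 or 20 points in an arm's composite proportion per misclassified patient at 10 v 5. The number of such patients is unknown.

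A reader might also infer a bias against the arm discharged sooner, or against alvelestat. The documents support no direction: it depends on which text is applied and on how stops are spread between arms.

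The conclusion assumes that ET/W means early termination or withdrawal, that the 10-day window applies to that component, and that the combined event in SAP 7.6 is the composite in 8.3.

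**What to change.** - Bring SAP 5.1, 5.2 and 5.5.1 into line with protocol 5.1 and 7.1: Days 1-5, with optional extension to Day 10.
- In SAP 8.3, spell out ET/W and define it as stopping before the end of the patient's planned course. Set that course by the protocol version in force: Day 10 under version 1.0; Day 5, or Day 10 if extended, under version 2.0. The version matters because protocol 5.5 refers to experience already gained in this trial, and Appendix 9 records that the course was 10 days before Amendment 1.
- State in 8.3 that Day 5 completion without extension, and stopping because of discharge alive, are not events, to match Table 7. Use the same planned course when deriving missed doses for Table 7.

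The cost is SAP wording before database lock. No new data are needed: dosing days and doses per day (SAP 5.7) and discharge dates (protocol 9.3) are already collected.

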5.5.2 Blinding

The UAB Research Pharmacy's unblinded pharmacist will label the study medication and perform accountability measures.

The blind will be broken only if specific emergency treatment would require knowing the treatment status of the patient or if the protocol review committee recommends unblinding data for safety review reasons. If the blind needs to be broken for an individual patient, the Investigator will contact the Sponsor as soon as feasible. The Investigator may unblind the study medication immediately if he/she feels it is necessary prior to contacting the Sponsor. However, the Investigator should promptly document and explain to the Sponsor any premature unblinding. Otherwise, all blinding will be maintained until all queries are resolved and the database is locked.

5.6 Prior and Concomitant Therapy

The Medical Monitor should be contacted if there are any questions regarding concomitant or prior therapy.

- UAB's standard treatment for COVID-19 infection is permitted, with the exception of prohibited medications listed below:
- Requirement for medications mainly metabolized by CYP2C9 and with narrow therapeutic index (eg, warfarin, phenytoin) is prohibited unless therapeutic monitoring available for duration of alvelestat dosing
- Medicines that are potent CYP3A4 inhibitors including (but are not limited to) clarithromycin, diltiazem, erythromycin, itraconazole, ketoconazole, ritonavir, verapamil

and potent inducers including but not limited to phenobarbital, phenytoin and rifampicin, will be exclusionary

- Requirement for medications substantially reliant on OATP1B1 for metabolism where discontinuation during study drug administration is not possible or where fluctuations in levels are considered clinically important (as per investigator judgement) and cannot be clinically monitored (e.g., statins, valsartan, olmesartan, enalapril, repaglinide)

5.7 Treatment Compliance

All days the study medication was received and the doses/day will be recorded on the appropriate eCRF. If study medication dose was missed, decreased or halted, the information will be recorded to track compliance.

6 DEFINITIONS

6.1 General

General clinical study definitions are listed in Table 2.

Table 2. COSTA clinical study general definitions.

Term	Definition for Study
Baseline	The most recent pre-dose assessment prior to first dose of study medication.
Clinical status assessment	Each assessment will be recorded as a number in the CRF based on the WHO Ordinal Scale status categories below. Where possible the timing of each assessment should be similar (i.e. morning or evening throughout). The Ordinal Scale is adapted from the WHO R&D Blueprint expert group which measures illness severity over time (https://www.who.int/blueprint/priority-diseases/key-action/COVID19_Treatment_Trial_Design_Master_Protocol_synopsis_Final_18022020.pdf) according to the following criteria: 
 0. Uninfected, no clinical or virological evidence of infection 1. Ambulatory, no limitation of activities 2. Ambulatory, limitation of activities 3. Hospitalized – mild disease, no oxygen therapy* 4. Hospitalized – mild disease, oxygen by mask or nasal prongs* 5. Hospitalized – severe disease, noninvasive ventilation or high flow oxygen* 6. Hospitalized – severe disease, intubation and mechanical ventilation 7. Hospitalized – severe disease, ventilation and additional organ support – vasopressors, renal replacement therapy, extracorporeal membrane oxygenation 8. Death
COVID disease severity	At baseline/randomization, the categorization of COVID-19 disease severity will be in accordance with the FDA's document: COVID-19: Developing Drugs and Biological Products for Treatment or Prevention Guidance for Industry (May 2020). 
 Mild disease (meeting all inclusion and no exclusion criteria): Symptoms of mild illness that could include fever, cough, sore throat, malaise, headache, muscle pain, gastrointestinal symptoms, without shortness of breath or dyspnea and no clinical signs indicative of moderate, severe, or critical severity.

Term	Definition for Study
	
 Moderate disease (meeting all inclusion and no exclusion criteria): could include any symptom of mild illness or shortness of breath with exertion. Clinical signs suggestive of moderate illness, such as respiratory rate \geq 20 breaths per minute, saturation of oxygen (SpO₂) $>$ 93% on room air at sea level, heart rate \geq 90 beats per minute and no clinical signs indicative of severe or critical severity. Severe disease (meeting all inclusion and no exclusion criteria): could include any symptom of moderate illness or shortness of breath at rest, or respiratory distress. Clinical signs indicative of severe systemic illness, such as respiratory rate \geq 30 per minute, heart rate \geq 125 per minute, SpO₂ \leq 93% on room air at sea level or PaO₂/FiO₂ $<$ 300 and no criteria of critical severity. Critical disease: evidence of critical illness, defined by at least one of the following: 1) respiratory failure defined based on resource utilization requiring at least one of the following: endotracheal intubation and mechanical ventilation, oxygen delivered by high-flow nasal cannula (heated, humidified, oxygen delivered via reinforced nasal cannula at flow rates $>$ 20 L/min with fraction of delivered oxygen \geq 0.5), noninvasive positive pressure ventilation, ECMO, or clinical diagnosis of respiratory failure (i.e., clinical need for one of the preceding therapies, but preceding therapies not able to be administered in setting of resource limitation); 2) shock (defined by systolic blood pressure $<$ 90 mm Hg, or diastolic blood pressure $<$ 60 mm Hg or requiring vasopressors); or 3) multi-organ dysfunction/failure.
Day	Calendar day
Day 1	
The day a patient received their first dose of study medication.
 
 If a patient received their 1st dose of study medication the day following randomization, the study day number will be adjusted so that Day 1 = 1st dose of study medication.
Discharge	
The patient is discharged and leaves the hospital alive. This does not include if a patient is moved to another unit.
 
 The time to discharge = the elapsed time (in days) from Day 1 to the earliest day at which the patient is Discharged from hospital (= Day where the Ordinal Scale score is equal to 1 or 2).
Improvement in clinical status	A decrease from baseline of at least one point in the Ordinal Scale score (eg, 5 to 4).
Worsening clinical status	An increase from baseline of at least one point in the Ordinal Scale score (eg, 5 to 6).

